5.1.2 Primary Outcome

The primary outcome of adherence to screening guidelines at 12 months for Hypotheses 1 and 2 will combine MRR and self-report by using MRR when available and self-report otherwise. We anticipate obtaining MRR and verification on screening tests at the 12-month survey. Participants will be asked to provide contact information on both their primary care physician and any specialist who provided a screening test, reducing the chance of missing a test that was conducted but not reported to the primary care physician. For those who are lost to follow-up, a signed MRR form will enable us to obtain the adherence outcome for those participants. Thus, we anticipate adherence for the overwhelming majority of patients will be based on MRR. [name] will supervise these analyses with assistance from [name].

For hypotheses 1 and 2, the differences in binary adherence (Hypothesis 1, all needed screenings; Hypothesis 2, any needed screening) across the three randomized arms will be tested initially with pairwise chi-square tests. Binary logistic regression analysis will be used to compare the two interventions

and the UC group on the binary dependent variable (adherence), while adjusting for any potentially confounding covariates. The models will be controlled for any demographic covariate (e.g., age, education) for which the randomized groups differ significantly at baseline using a liberal significance level of 0.20 to achieve conservative adjustment. As a sensitivity analysis, multiple imputation will be used to impute the adherence outcome for participants who are lost to follow-up and did not sign a MRR. We plan to include screening history as a covariate in our analysis by using the total number of past screenings for each test since the participant turned 50. All variables in the logistic regression models will be tested using the likelihood ratio test.³⁷ Adjusted odds ratios (ORs) and profile-likelihood-estimated 95% confidence intervals for those ORs will be provided. Our proposed theoretical model includes only variables that can be measured and used in modeling. The conceptual model (Figure 2) uses constructs from the Theory of Reasoned Action, and Theory of Planned Behavior, as well as other well-established behavioral theories.²⁵⁻²⁸ Our model has taken these theories into consideration and added important constructs such as engagement. Therefore, we will perform theoretical modeling using structural equation modeling using the MPLUS software, as described in the next section. We have labeled this section as exploratory analyses because it is not part of the primary aims; however, the results will provide insightful findings about the context of the intervention effects including how all the theoretical variables interact with each other, both in terms of mediation and moderation effects.

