3.3 Randomization

Once eligibility is confirmed via medical record review, participants will be randomly assigned to one of 3 study arms -1)TIDVD alone, 2)TIDVD + PN, or 3)UC. A centralized web-based system at OSU will be used to randomize participants to one of the 3 study arms. Randomization will be stratified by age (50-64 vs. 65-74) and by seven screening categories representing which screening test(s) each woman needs (BC, CC, CRC, BC+CC, BC+CRC, BC+CC+CRC, or CC+CRC).

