5.0 Data Handling and Analyses

5.1 Statistical Analysis

5.1.1 Sample Size

Estimates of effect size (Table 5) for the intervention at 12 months is based on our experience in projects promoting screening among underserved populations. We estimate 10% attrition at 12 months, when our primary outcome will be assessed. Attrition of 10% is conservative because we will have medical record data on most of the persons who drop out which will reduce the effect of drop out on the primary outcomes. We based power calculations on 2-sided tests when comparing the two intervention arms (TIDVD vs. TIDVD+PN) because we could not be certain which group would perform better. Because of the overwhelming evidence in the literature^{35,36} that the UC arm does not have better screening rates than tailored DVD or PN interventions, we based the power calculations on 1-sided tests for comparisons to the control group (TIDVD vs. UC; TIDVD+PN vs. UC). The planned statistical analyses are consistent with these power calculations. Specifically, we will use two sided tests for TIDVD vs. TIDVD+PN, and the 1-sided tests for comparing interventions to the UC arm, using the 1-sided p-value from the Z statistic in contingency table analysis and from the likelihood ratio test in logistic regression analysis. To achieve 80% power for the contingency table analyses, and the likelihood ratio tests of logistic regression for the primary outcome of adherence to all needed screening tests at 12 months by MRR, a sample size of 356 per each intervention group and 180 in the UC group will be needed, which will require 396 per intervention group and 200 in the UC group at baseline to account for attrition. For 80% power for the secondary outcome of adherence to any needed (BC or CC or CRC) test, regardless of the number of screening tests needed, a sample size of 376 per each intervention group and 200 in the UC group will be required at 12 months. We will require 418 per intervention group and 222 in the UC group at baseline to account for attrition and to achieve at least 80% power for both outcomes. The total sample size is 1058 participants enrolled with 418 randomized to each intervention arm and 222 randomized to the UC arm.

Table 5.	Samp	le Size'
----------	------	----------

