Effect sizes for screening at 12 months	Control (UC) 12 Months	TIDVD 12 months	TIDVD+ PN 12 months	TIDVD+PN at baseline for	control arm (UC) at baseline for 80% power at 12 months	TIDVD+PN	-	Power TIDVD vs. TIDVD+ PN	TIDVD vs. control	Power TIDVD+ PN vs. Control (UC)
Cervical	35%	50%	70%	NA	NA	NA	NA	NA	NA	NA
Breast	35%	45%	65%	NA	NA	NA	NA	NA	NA	NA
Colon	30%	40%	55%	NA	NA	NA	NA	NA	NA	NA
All needed screenings (primary outcome)	10%	20%	30%	396	200	356	180	82%	83%	99%
Any (at least 1) needed screening (secondary outcome)	25%	35%	45%	418	222	376	200	80%	80%	99%

*Estimates of effect sizes for the secondary outcome (at least 1 needed test adhered to by 12 months) was based on the most conservative single test (i.e., colon cancer screening). Effect sizes for the primary outcome were based on an estimated reduction of 5% in the number of participants who would adhere to all needed tests compared to only one of the needed tests. Power columns are based on the most stringent required sample size, i.e., when N=418 per each intervention arm and N=222 controls at baseline and projected 376 per each intervention arm and 200 controls at 12 months.

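### The randomization strata (age group, screening need) are not committed terms in the primary analysis; fixing them and the covariate list in advance is a cheap refinement whose small power gain the documents cannot pin down

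*Combined protocol and SAP*

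**What the plan says.** Section 3.3: "Randomization will be stratified by age (50-64 vs. 65-74) and by seven screening categories". The categories record which of the three tests each woman is missing. No allocation method within strata is given.

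Section 5.1.2: differences in adherence across arms "will be tested initially with pairwise chi-square tests". A logistic model then compares the arms "while adjusting for any potentially confounding covariates". The rule for choosing them is: "The models will be controlled for any demographic covariate (e.g., age, education) for which the randomized groups differ significantly at baseline", with significance judged at 0.20. Screening history is also planned as a covariate, "using the total number of past screenings for each test since the participant turned 50".

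Section 5.1.1 bases power and testing on two methods for the same primary outcome: the Z statistic from the contingency table and the one "from the likelihood ratio test in logistic regression analysis". It does not say which decides the trial. On the numbers followed up: "We estimate 10% attrition at 12 months, when our primary outcome will be assessed".

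**The concern.** The usual principle is that the analysis should follow the randomization. Here the chi-square test ignores the strata, and the logistic model reaches them only by accident. Screening need is not a demographic variable, so the 0.20 rule does not cover it. Age is named only as an example within that rule, and age group is a factor that stratification is meant to balance.

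Need is also the baseline factor most closely tied to the primary outcome: completing all needed tests is easier for a woman who needs one than for a woman who needs three. Screening history does not replace it. A count since age 50 grows with age, and because the intervals in Table 1 range from one to ten years, the count does not show which tests are due.

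At stake are some power and, more importantly, a model whose covariates are known before the data are seen.

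**Working it through.** **1. Which terms are committed**

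| Factor | Randomization (3.3) | Chi-square (5.1.2) | Logistic model (5.1.2) |
|---|---|---|---|
| Age group | stratified | absent | only if selected |
| Need, seven categories | stratified | absent | not reached by the 0.20 rule |
| Screening history | no | absent | planned |
| Other demographics | no | absent | only if they differ at p<0.20 |

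**2. The plan's own power.** Inputs from Table 5: 376/376/200 women at 12 months; all-needed rates 10% (UC), 20% (TIDVD), 30% (TIDVD+PN). Power = Φ[(|p2−p1| − z·SE0)/SE1], with SE0 pooled and SE1 unpooled.

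- 20% vs 30%: SE0 = √(0.25×0.75×2/376) = 0.0316; SE1 = √((0.16+0.21)/376) = 0.0314. Two-sided 0.05 gives 88.8%; two-sided 0.025 gives 82.4% (stated 82%).
- 10% vs 20%: pooled rate (20+75.2)/576 = 0.165; SE0 = 0.0325; SE1 = √(0.09/200+0.16/376) = 0.0296. One-sided 0.05 gives 94.2%; one-sided 0.0125 gives 82.0% (stated 83%).

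The primary row therefore reproduces at about half of 5%. The secondary row gives 80.0% and 80.0% at 5%, as stated. No test alpha is written down, so both levels are used below.

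**3. How strongly need predicts the outcome.** With Table 5's UC rates, a woman needing one test has a 30–35% chance of completing it. A woman needing three has 0.35×0.35×0.30 = 3.7% if tests are independent. She has about 9% with a latent correlation of 0.34, the value that reproduces Section 2.1's 8.6% on all three tests from 32%, 36% and 30%.

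Table 5 cannot settle the gradient, because its rows conflict. Completing any needed test cannot be rarer than completing the least-used single test, yet the any-needed row shows 25/35/45% against 30/40/55% for colon. The footnote describes a 5-point gap between any and all; the printed gap is 25−10 = 35−20 = 45−30 = 15 points.

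**4. Power gain: stratified Cochran-Mantel-Haenszel (CMH) minus unstratified Z test.** Simulated at 376/376/200. For the matched row, uptake was fitted to the all-needed and any-needed rates (printed rows and footnote gap), with assumed mixes of women needing 1/2/3 tests of 40/35/25, 60/25/15 and 25/35/40%. The per-test rows also use a mix derived from Section 2.1 and a mostly-single-need mix, with overall rates scaled to 10/20/30%.

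| Assumption | Gain at 5% (points) | Gain at half of 5% (points) |
|---|---|---|
| Strata not prognostic | about 0 | about 0 |
| Matched to all-needed and any-needed rows | −0.1 to +0.8 | about 0 to +1.9 |
| Tests correlated, from Section 2.1 | +0.2 to +1.8 | +1.0 to +2.3 |
| Tests independent | +0.4 to +2.7 | +1.6 to +4.7 |

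Simulation error is at most 0.07 point for the matched row at 5%, and roughly 0.3 to 0.5 for the scaled per-test runs.

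If the likelihood ratio test already contains screening history (TIDVD vs TIDVD+PN, 5%, matched rows, assumed odds ratio of 1.0 to 1.2 per past screen), adding seven categories and age group gives +0.1 to +0.9 point.

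**5. Size at nominal 5%.** On the matched rows: unstratified Z 4.5–5.1%, CMH over 1/2/3 tests 4.7–5.1%, seven-category likelihood ratio test 5.1–5.4%. Under the steepest gradient tried: 4.0%, 4.8–5.4% and 5.3–5.6%.

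**6. The 0.20 rule.** An unstratified demographic enters about one time in five (430 of 2,000 simulated trials, 21.5%). With five independent demographics (an assumption), at least one enters with probability 1−0.8⁵ = 67%. Age group was selected in 0 of 2,000 trials with assumed blocks of 20 in 14 strata, and in 21.5% with no restriction within strata.

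**7. Sparse cells.** UC expects 0.10×200 = 20 events: 20/7 = 2.9 per need category on average and 20/14 = 1.4 per age-by-need cell.

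**The case against.** The strongest reply is that this is a preference. The plan already allows adjustment for any potential confounder, names age, and includes past screenings for each test. The unadjusted test is valid, and the simulated gain can be nil. This is right about validity. It does not close the gap, because a general permission to adjust is not a commitment, and nothing names need.

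A second objection is that no single gain can be claimed on Table 5's rates. This stands. Fitting the all-needed and any-needed rows forces single-test uptake to no more than 25/35/45%, which contradicts all three per-test rows. The per-test rates under independence give all-needed rates of 13.7–23.3%, 21.9–33.4% and 39.8–51.7% across the three mixes, above the printed 10/20/30%. Alpha matters too, because power near 90% or more leaves little room for gain.

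Third, the finding that age group would almost never trigger the 0.20 rule rests on assumed blocking. This also stands, and the point does not depend on it.

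A reader might go further and infer that ignoring the strata invalidates the primary test or puts the planned power at risk. The documents do not support that. The error is in the conservative direction and small, and every simulated stratified analysis had about the same power or more.

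**Conclusion.** The point holds as a minor, low-cost improvement. Neither stratification factor is a committed model term, and the 0.20 rule lets chance imbalance choose the demographics. The unstratified test is at most slightly conservative, and the stated 80% power is not threatened.

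The documents leave the size of the gain open: they give no alpha, need mix or correlation between tests, and Table 5's rows disagree. A fair statement is 0–1 point at 5% on the all-needed and any-needed rows, about 0–2 under other alphas or correlated per-test rates, and 3–5 at most near independence. The main argument is an analysis that follows the randomization and is fixed in advance. Power is secondary, and the interval for the conditional odds ratio will not generally narrow.

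**What to change.** In Section 5.1.2:

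- Name one primary test. Either use a logistic likelihood ratio test with arm, age group and screening need as fixed terms, or a CMH test over need collapsed in advance to 1, 2 or 3 tests needed. The 14 age-by-need cells would be too sparse in UC for the CMH test.
- If the seven categories are kept in the logistic model, state beforehand how sparse ones will be merged.
- Replace the 0.20 rule with a fixed covariate list that keeps screening history.
- Keep the unadjusted chi-square as supportive.
- Report a standardized risk difference beside the conditional odds ratio.

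The cost is SAP wording, since both factors are already needed to randomize. There are three downsides. The odds ratio becomes conditional on the strata. Sparse UC cells make the collapsing rule necessary. The seven-category likelihood ratio test runs slightly above nominal size, so the CMH option is the safer one if strict size control is wanted.

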5.1.3 Exploratory Aims

Associations between theoretical variables (community, social, and individual) and the binary screening outcomes will be identified with non-linear mixed models, accounting for two levels of assessment. The first level includes variables measured at the person level such as individual demographic and screening history variables, as well as beliefs which are measured for each participant in this study. The second level includes community variables measured at the county level such as number of providers, number of screening facilities, deprivation index, and median income level. Moderators of intervention effects on adherence will be identified by testing interaction terms in the model. The theoretical model in Figure 4, including mediation effects, will be tested with structural equation models using the MPLUS software.³⁸

Most recently recorded height and weight will be collected from any medical providers an individual provides to us to contact for cancer screening history. Height and weight will be used to calculate body mass index (BMI) to compare the association of BMI status and the concordance of self-report and medical record review as it relates to screening adherence for breast, cervical and colorectal cancers. Demographic and behavioral factors (such as age and smoking status) may modify associations between BMI and concordance of self-report and medical record review-confirmed cancer screening adherence; relationships between those variables and BMI and cancer screening adherence will be investigated.

5.2 Evaluation of Cost-Effectiveness

[name] will assume responsibility for the cost-effectiveness analyses. The proposed economic evaluation of interventions can be seen as addressing three questions:

- 1) what are the full costs associated with the implementation of the interventions (cost-identification analysis);
- 2) what are the net costs associated with the interventions (is each intervention actually cost-saving?); and
- 3) what is the cost-effectiveness of each intervention?

5.2.1 Cost of the Interventions

The first question is answered by a careful accounting of the operational costs of the interventions, excluding those costs that are purely attributable to the research. Some of these are fixed costs associated with hiring and training PN's (which may recur if there is turnover in the position), and others are ongoing costs associated with the delivery of services. In the model implemented in this study, the PN's spend full time in that activity. Thus, the costs of implementation are straightforward and obtainable. Even though the PN is full-time, we will want to collect data concerning at least the broad categories of time use, so that we can estimate the cost of specific components (e.g., arranging transportation) more accurately. The best way to do this will be a structured time log. We will use a developed Participant Encounter Form and a Tracking Log of Direct Participant Contacts that will provide the majority of this information. The procedures outlined above will establish the aggregate cost of implementation. However, it will also be useful to measure cost on a per-unit basis. This will be done by calculating average cost per active participant per month and average cost per participant for cancer screening completion, for each test, type of test, and

all needed tests.

5.2.2 Cost Savings

The second question is whether each intervention is actually cost-saving, and is essentially an attempt to calculate the numerator in a typical cost-effectiveness analysis:³⁹ the change in cost attributable to each intervention. Using the terminology of Gold et al., a full assessment would require measuring the changes in use of health care resources, changes in use of non-health care resources, changes in use of informal caregiver time, and changes in use of participant time for cancer screening.³⁹ In order to avoid distortions in the measured impact of an intervention due to pricing differences, all cancer screening tests will be assigned cost based on their Medicare allowable payment, regardless of how the service was actually paid for. Medicare payments are often used as a proxy for cost in cancer studies.^{40,41} While this is not a pure cost measure, it is comparable and avoids other potential distortions like differences in cost to charge ratio for different payors.

5.2.3 Cost Effectiveness

The third question, the cost-effectiveness of each intervention, will be the most difficult to address. Because of the nature of the interventions and the limited time for observation, it is not likely that the interventions will have a significant impact on standard measures of effectiveness used in cost-effectiveness analysis, such as quality-adjusted life years (QALYs). Cost-effectiveness analysis (CEA) implies a comparison of whether the cost per unit of outcome in one situation exceeds that in another. Unless the outcome measures are comparable, this is not possible. We will be able to examine outcomes of the interventions and the UC group (completed cancer screening tests). Our analysis will emphasize the first two questions (cost of the intervention itself, calculation of net cost). CEA will consist of measuring the incremental cost of achieving the observed incremental outcomes, but not a cost-effectiveness ratio in standard terms. Cost Utility: From our cost effectiveness estimates, we will conduct a QALY-based (Quality Adjusted Life Year) cost utility analysis. Calculating QALYs will require both utility (quality) weights and estimates of the life years saved. Both utility weights and the life years saved from the health outcomes will be drawn from the published literature. The Markov modeling will be conducted in TreeAge. [name] will conduct these analyses.

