1.3 Aims and Hypotheses

The specific aims are to:

- Aim 1: compare the effectiveness of a tailored and interactive DVD (TIDVD) vs. TIDVD + telephone-based PN intervention (TIDVD + PN) vs. UC, to increase guideline-based cancer screening rates at 12 months post randomization for BC, CC, and CRC among 1058 women age 50 to 74 living in rural northwest Ohio and northeast Indiana
- **Hypothesis 1:** Women in the TIDVD+TPN group will have higher rates of within guideline adherence to all screening tests via MRR at 12 months compared to those who receive the TIDVD alone or UC.
- **Aim 2:** compare the cost effectiveness of the TIDVD and the TIDVD + PN intervention vs. UC, for adherence to each screening outcome or combination of screening tests.
- **Hypothesis 2:** The TIDVD + TPN intervention will be more cost-effective than the TIDVD intervention or UC for adherence to each or combination of screening tests.

We will also identify associations between theoretical variables (community, social, and individual) and screening outcomes, including interactions with the interventions. If found to be cost effective, either or both interventions have the potential to be immediately disseminated to increase BC, CC, and CRC screening rates and ultimately reduce cancer disparities for underserved rural women. This project will use an overall theoretical framework to understand health disparities that includes individual, social and community level variables, and a conceptual model for the intervention which uses a multiple behavior theoretical approach, all of which have demonstrated efficacy in improving adherence to single screening test behaviors, as well as other preventive health behaviors.

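### Hypothesis 2 claims superior cost-effectiveness, but no economic output has an uncertainty measure or a criterion, and section 5.1.2 attaches the Hypothesis 2 label to something else

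*Combined protocol and SAP*

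**What the plan says.** Section 1.3 sets two aims, each with a directional hypothesis. The second reads: "The TIDVD + TPN intervention will be more cost-effective than the TIDVD intervention or UC for adherence to each or combination of screening tests".

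Section 5.2 plans four economic outputs:
- **Unit cost (5.2.1):** "average cost per participant for cancer screening completion, for each test, type of test", and for all needed tests.
- **Net cost (5.2.2):** "the change in cost attributable to each intervention", with every screening test priced at its Medicare allowable payment.
- **Incremental analysis (5.2.3):** "CEA will consist of measuring the incremental cost of achieving the observed incremental outcomes, but not a cost-effectiveness ratio in standard terms".
- **Cost-utility (5.2.3):** "From our cost effectiveness estimates, we will conduct a QALY-based (Quality Adjusted Life Year) cost utility analysis", with utility weights and life years taken from the literature. "The Markov modeling will be conducted in TreeAge".

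The only intervals named in the analysis plan are in section 5.1.2 and concern adherence: "profile-likelihood-estimated 95% confidence intervals for those ORs will be provided". The only sensitivity analysis named is multiple imputation of the adherence outcome, in the same section. Section 5.1.2 also defines Hypothesis 1 as adherence to all needed screenings and Hypothesis 2 as adherence to any needed screening, both tested first with pairwise chi-square tests.

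**The concern.** A directional hypothesis needs a quantity, a measure of its uncertainty and a rule for when it is supported. For the cost-effectiveness hypothesis, section 5.2 supplies candidate quantities but neither of the other two. The one place that assigns a test to Hypothesis 2 means a different hypothesis by it, so the section 1.3 version has no test.

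Aim 2 is therefore at stake. An incremental ratio has an estimated difference in its denominator and can be imprecise even when the adherence comparison is adequately powered. The QALY model starts from the same estimates and adds literature inputs, so unreported uncertainty would pass straight into it. A reader could not tell a firm finding from a ranking that another sample might reverse.

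**Working it through.** **Passages side by side.** Sections 5.2 to 5.2.3 name no confidence interval, bootstrap, deterministic or probabilistic sensitivity analysis, acceptability curve, value per additional woman screened, or decision rule. The odds-ratio intervals and the imputation in 5.1.2 cover adherence and do not extend to costs.

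**The plan's own figures.** The documents give no cost, cost variance, threshold or power for the cost-effectiveness hypothesis, so there is no stated figure to reproduce. What follows illustrates size only.

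**Inputs.** Table 5, all needed screenings: UC 10%, TIDVD 20%, TIDVD+PN 30%. Section 5.1.1 and the Table 5 footnote: 376 per intervention arm and 200 in UC at 12 months. Assumption: C, the added intervention cost per woman of TIDVD+PN over TIDVD, is fixed and known.

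**Interval for the difference**
- Difference = 0.30 − 0.20 = 0.10
- SE = √(0.30×0.70/376 + 0.20×0.80/376) = 0.0314
- 95% limits = 0.10 ± 1.96×0.0314 = 0.0385 to 0.1615, or 3.9 to 16.1 points

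**Intervention cost per additional adherent woman (C ÷ difference)**
- Point estimate: C/0.10 = 10C
- Limits: C/0.1615 = 6.2C and C/0.0385 = 26.0C
- Upper over lower: 26.0/6.2 ≈ 4.2

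**With screening-test costs.** Section 5.2.2 prices the tests, so the numerator rises with the number of women screened. If each additional adherent woman brings test cost k, the ratio is roughly C/difference + k. With C = $50 and k = $400 (both assumed), the limits are 310 + 400 = $710 and 1,298 + 400 = $1,698, a 2.4-fold range. The relative range shrinks as k grows relative to C.

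**Stability of a point-estimate ranking.** I simulated 400,000 trials with binomial outcomes at 10/20/30% and 200/376/376 women. Costs were fixed, both interventions were compared with UC, and TIDVD+PN was assumed to cost r times TIDVD. Test costs were left out.

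| r (assumed) | True ratio vs UC, in TIDVD costs: TIDVD | TIDVD+PN | Trials ranking TIDVD+PN better |
|---|---|---|---|
| 1.5 | 1/0.10 = 10 | 1.5/0.20 = 7.5 | 89% |
| 2 | 10 | 2/0.20 = 10 | 50% |
| 2.5 | 10 | 2.5/0.20 = 12.5 | 22% |
| 3 | 10 | 3/0.20 = 15 | 10% |

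The Table 5 footnote places the primary rates five points below the secondary 25/35/45%, that is 20/30/40%. At those rates the last figure is 14%.

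**The case against.** The strongest reply is that the plan contains more than its incremental sentence suggests. Much of that reply stands.

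- **A reader might infer that incremental cost is all the plan offers.** It is not. Unit cost, net cost and a QALY-based Markov analysis are also planned. None of them carries an uncertainty measure, so the gap remains.
- **A reader might infer that the disclaimer rules out any usable ratio.** Section 5.2.3 uses the QALY as its example of a standard effectiveness measure, so the disclaimer can be read as excluding only cost per QALY. Incremental cost and incremental outcome are already the two parts of a cost per additional woman screened.
- **A reader might infer that being more cost-effective than UC has no meaning here.** An increment measured against UC is a comparison with UC. What is missing is a value per additional woman against which to judge it.
- **A reader might infer that the plan will declare the arm with the smaller ratio the winner, and that dissemination hangs on that ranking.** No section states such a rule, and 5.2.3 says the emphasis will fall on intervention cost and net cost. Section 2.3 ties dissemination of either or both interventions to cost-effectiveness compared with UC, not to ranking the two interventions.
- **A reader might take the roughly four-fold range as a minimum.** It is not. It holds only with test costs left out of the numerator, although 5.2.2 prices them.

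Nothing in this reply supplies an interval or a criterion for Hypothesis 2, or resolves its two definitions.

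**Conclusion.** The concern holds in a limited form. No economic result in sections 5.2.1 to 5.2.3 has an uncertainty measure or a criterion, and Hypothesis 2 means different things in 1.3 and 5.1.2. As written, the cost-effectiveness claim would rest on point estimates.

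The range of 6.2 to 26.0 times the added intervention cost rests on Table 5's printed rates, 376 women per arm, a fixed cost difference and no test costs. Including test costs narrows the relative range by an amount that depends on prices the documents do not give. The ranking percentages rest on assumed cost ratios; they show that ranking is unreliable when the ratio is near 2, not that this trial lies there.

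The adherence analyses are unaffected. This should be corrected because Aim 2 cannot be concluded as the plan stands.

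**What to change.** In 5.2.3, replace the incremental sentence with a specification along these lines:

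1. Report incremental cost per additional woman adherent to all needed tests. Compute it sequentially: TIDVD versus UC, then TIDVD+PN versus TIDVD, after removing dominated options.
2. Bootstrap each woman's cost and outcome together within arm. Report 95% intervals and an acceptability curve over a stated range of values per additional woman screened.
3. Carry the bootstrap draws into the Markov model and add sensitivity analysis of the literature inputs.
4. Claim Hypothesis 2 only where the uncertainty supports it. One workable form requires the interval for the incremental net benefit of TIDVD+PN to exclude zero against each comparator over a stated range of values.
5. Do not base the claim on the point-estimate ranking, or merely on the highest probability of being optimal. In simulations at Table 5's printed rates (fixed costs, cost ratios 2 and 3, value per woman 8 to 25 times the TIDVD cost), the latter rule chose the same arm as point-estimate net benefit in 98 to 100% of trials. It could name TIDVD+PN with a probability as low as 34%.
6. In 5.1.2, relabel the any-needed-screening comparison so that Hypothesis 2 refers only to cost-effectiveness.

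The navigator time and encounter records (4.3.1, 5.2.1) and the uniform test prices (5.2.2) are already planned, so no new data collection is needed. The cost is plan wording, a few more analysis runs and the need to state a range of values per woman screened. The downside is that Hypothesis 2 becomes harder to claim.
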